	
For confidence interval involving binary outcomes, the Cochran-Mantel-Haenszel weights will be used to combine the stratum-specific differences where the strata will be based upon the factors used to assign subjects to treatment for involving continuous outcomes, the stratum-specific differences will be combined using an analysis of variance approach with weights proportionate to the stratum sizes.
 
Other secondary continuous variables will be summarized using descriptive statistics (N, mean, standard deviation, 95% confidence interval, median, range, minimum, and maximum, where appropriate). Discrete variables will be summarized using frequency counts and percentages.
 
Starting with Treatment Period 2, data summaries for efficacy will be presented by the particular treatment sequence received in Treatment Periods 1 and 2: CHS-1420/CHS-1420, Humira/Humira and Humira/CHS-1420. Safety data for Treatment Period 1 will be presented by the treatment received. Safety data for the study period as a whole (ie, time spanning Treatment Periods 1 to 3) will be presented for those randomized and receiving the same treatment in Treatment Periods 1 and 2. Separate summaries will be presented for Treatment Period 2 based upon the particular treatment sequence received in Treatment Periods 1 and 2: CHS-1420/CHS-1420, Humira/Humira and Humira/CHS-1420. Safety data for the open-label extension (Treatment Period 3) will be summarized based primarily upon events first recorded (or worsened in severity) during the open-label extension.

Study Duration	
Screening: up to 28 days
 
Treatment Period 1: 16 weeks (Week 0 to Week 16)
 
Treatment Period 2: 8 weeks (Week 17 to Week 24)
 
Treatment Period 3: 24 weeks (Week 25 to Week 48)
 
Follow-up: 8 weeks after last dose of study drug
 
Subjects may be considered completers if the subjects complete 48 weeks of treatment and the Follow-up visit 8 weeks following the last dose in this trial (completes the study);
 
Subjects may be withdrawn from study therapy for any of the following reasons:
 
• The subject experiences a serious adverse event (SAE) or medically important AE (e.g., serious or opportunistic infection) that would preclude further treatment with study drug;

[figure not shown]

Figure 1: Study Design

[figure not shown]

TABLE OF CONTENTS

SYNOPSIS	4
TABLE OF CONTENTS	13
LIST OF TABLES	15
LIST OF FIGURES	16

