6.1.2 Secondary Efficacy Variables

The secondary efficacy endpoints are

- PASI-75 at Weeks 2, 4, 6, 8, 10, 16, 20, 24, 32, 40 and 48;
- Percentage changes in PASI from Baseline at Weeks 2, 4, 6, 8, 10, 12, 16, 20, 24, 32, 40 and 48;
- 50% improvement in Psoriasis Area and Severity Index (PASI-50) at Weeks 2, 4, 6, 8, 10, 12, 16, 20, 24, 32, 40 and 48;
- 90% improvement in Psoriasis Area and Severity Index (PASI-90) at Weeks 2, 4, 6, 8, 10, 12, 16, 20, 24, 32, 40 and 48;
- Changes in PSGA of disease activity on a scale from 0 to 5 from Baseline to Weeks 2, 4, 6, 8, 10, 12, 16, 20, 24, 32, 40, 48 and, as applicable, the Follow-up or ET visit;
- Change in PSGA = 0 to 1, demonstrating clear or almost clear skin at Weeks 2, 4, 6, 8, 10, 12, 16, 20, 24, 32, 40 and 48 and, as applicable, the Follow-up or ET visit;

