8.1.4 Per Protocol Population

The Per Protocol Population is defined as those subjects in the FAP completing at least 12 weeks of treatment and follow-up with respect to the PASI and have no protocol violations that may affect the interpretation of the primary efficacy endpoint. These violations will be identified by the Sponsor prior to study unblinding.

Subjects will be allocated to the treatment arm they are randomized to for a particular Treatment Period of analysis.

8.1.5 Open Label Extension Population:

The Open Label Extension Population is defined as those subjects receiving at least 1 dose of open label treatment. Subjects will be allocated to the treatment arm they received in Treatment Period 2.

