8.2.2 Efficacy Analysis

The primary statistical analyses will be based on:

- The difference between the percentages of subjects in the CHS-1420 and Humira groups achieving PASI-75 at Week 12.

Equivalence will be based upon the 95% (2-sided) confidence interval for the difference in PASI-75 rates. If both the lower and upper bounds of the 95% confidence interval exclude $\pm 15\%$ (inclusive), equivalence will be established. The mean percent change in PASI from Baseline to Week 12 between the CHS-1420 and Humira (US) groups will be assessed as a supporting secondary endpoint.

Subjects who lack a PASI assessment at Week 12 will be considered non-responders in the primary analyses. As a sensitivity analysis, the last available score will be used.

For PASI-75 at Week 12 (as well as for other binary outcomes where formal evaluations are made, if applicable), Cochran-Mantel-Haenszel weights will be used to combine the stratum specific differences ([LaVange, Durham, & Koch, 2005](#)) formed by the randomization strata.

For the percent change in PASI from Baseline (as well as for other continuous outcomes where formal evaluations are made, if applicable), the stratum-specific differences will be combined using an analysis of variance approach with weights proportionate to the stratum sizes.

Other secondary continuous variables will be summarized using descriptive statistics (N, mean, standard deviation, 95% confidence interval, median, minimum, and maximum) and discrete variables will be summarized using frequency counts and percentages.

For data collected after the start of Treatment Period 2, data summaries for efficacy will be presented by the particular treatment sequence received in Treatment Periods 1 and 2: CHS-1420/CHS-1420, Humira/Humira and Humira/CHS-1420.

For data collected during the open label extension, only descriptive data summaries will be presented. These summaries will be presented by the particular treatment received in Treatment Period 2, regardless of treatment received in Treatment Period 1.

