8.2.3 Safety Analysis

Safety data will be summarized and listed. No inferential statistical analyses of the safety data are planned. All safety summaries and listings will be generated using the Safety Population based upon treatment received for the Treatment Period of interest.

Safety data through Week 16 will be presented by the treatment received (CHS-1420 or Humira). Safety data for the study as a whole will be presented for subjects receiving CHS-1420 during Treatment Period 1 and those receiving

Humira during Treatment Period 1. Separate summaries will also be presented for Treatment Period 2 based upon the particular treatment sequence received in Treatment Periods 1 and 2: CHS-1420/CHS-1420, Humira/Humira and Humira/CHS-1420.

Safety data for the open label extension will be summarized separately. The primary focus of these summaries will be events that are recorded after beginning open-label treatment and events that began in Treatment Period 1 or 2 and worsen in severity in Treatment Period 3. The events will be summarized by treatment received in Treatment Period 2 and overall.

Adverse events will be coded and classified by system organ class and preferred term using the Medical Dictionary for Regulatory Activities (MedDRA). Data summaries will be based on TEAEs. All TEAEs will be listed and summarized by the subjects' treatment group (Treatment Period specific) when the events were reported. A summary of all drug-related AEs will also be generated. If there are any SAEs or any AEs leading to the discontinuation of study drug, a separate data listing will be generated.

Clinical laboratory data will be summarized descriptively and listed by treatment (Treatment Period specific) group. The change from pre-dose to the end of the study will also be summarized. For selected laboratory assessments, the frequency of abnormal values will be tabulated where abnormal ranges are available.

Prior and concomitant medications will be coded with the World Health Organization Drug Dictionary (WHO-DD) and listed. All concomitant medication taken after first dosing of study drug will be summarized.

Vital sign and ECG data will be summarized and listed by dose group and visit.

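### Section 8 gives Humira-to-CHS-1420 switchers no separate summary after Week 24, and the synopsis groups open-label efficacy and whole-study safety differently

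*Combined protocol and SAP*

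**What the plan says.** **Open-label efficacy.** Section 8.2.2 first gives a general rule: "For data collected after the start of Treatment Period 2, data summaries for efficacy will be presented by the particular treatment sequence received" in Periods 1 and 2, with three sequences named (CHS-1420/CHS-1420, Humira/Humira, Humira/CHS-1420). The next paragraph gives a rule for the open-label extension: "These summaries will be presented by the particular treatment received in Treatment Period 2, regardless of treatment received in Treatment Period 1". Section 8.1.5 defines the Open Label Extension Population in the same way: "Subjects will be allocated to the treatment arm they received in Treatment Period 2". The synopsis (Statistical Analysis) has only the sequence rule: "Starting with Treatment Period 2, data summaries for efficacy will be presented by the particular treatment sequence received in Treatment Periods 1 and 2". It makes no exception for Period 3.

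**Open-label safety.** Section 8.2.3 says: "The events will be summarized by treatment received in Treatment Period 2 and overall". The synopsis says which events count but names no grouping.

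**Whole-study safety.** In the synopsis, safety over Periods 1 to 3 "will be presented for those randomized and receiving the same treatment in Treatment Periods 1 and 2". Section 8.2.3 instead says: "Safety data for the study as a whole will be presented for subjects receiving CHS-1420 during Treatment Period 1 and those receiving" Humira in that period.

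**Antibodies.** Section 7.2.11 plans comparisons that include Weeks 32, 40 and 48. Section 8.2.4 summarises by treatment received and names no period.

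**The concern.** The efficacy and safety of switching is part of the secondary objectives (Section 2). The secondary endpoints run into the extension: "PASI-75 at Weeks 2, 4, 6, 8, 10, 16, 20, 24, 32, 40 and 48" (Section 6.1.2). Under Section 8, subjects who switched at the start of Period 2 and continue into Period 3 share a column with subjects who were never on Humira. A late difference in switchers would therefore appear only in diluted form.

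The wording also leaves the tables unsettled. For open-label efficacy, a programmer working from the synopsis builds three columns and one working from Section 8 builds two. For whole-study safety, the two texts admit different subjects to the same table.

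**Working it through.** **1. Planned group sizes.** Section 8.3 gives about 500 subjects, about 250 per arm. Section 4.3 gives 2:1:1 allocation.
- CHS-1420/CHS-1420: 500 × 2/4 = 250
- Humira/Humira: 500/4 = 125
- Humira/CHS-1420: 500/4 = 125

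The sample size is not in question. With 70% response in both arms, a 15-point margin and a 95% interval, n = 2 × 0.70 × 0.30 × (1.960 + 1.645)² / 0.15² = 243 per arm. Power at 250 is 91.1%. Both agree with the stated 250 and 90%.

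**2. The rules side by side.** Counts are randomised maxima and assume nobody leaves before Period 2. Period 3 numbers will be lower, because entry requires PASI-50 at Week 24 (Section 3.1).

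| Display | Synopsis | Section 8 |
|---|---|---|
| Open-label efficacy | Three sequences: 250 / 125 / 125 | Period 2 drug: CHS-1420 375, Humira 125 |
| Open-label safety | No grouping named | Period 2 drug, plus overall: 375, 125 |
| Whole-study safety | Same drug in Periods 1 and 2: CHS-1420 250, Humira 125 | Period 1 drug: CHS-1420 250, Humira 250 |

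**3. Switcher share and dilution.** The share is s = 125 / (125 + 250) = 0.333. If switchers differ from never-switched subjects by D, the pooled column moves by s × D. Neither D nor retention is given in the documents. If retention is assumed to differ between the two groups within 70% to 95%:
- 70% of switchers, 95% of never-switched: 87.5 / (87.5 + 237.5) = 0.269
- 95% of switchers, 70% of never-switched: 118.75 / (118.75 + 175) = 0.404

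An illustrative D of 10 points then shows as 3.3 (2.7 to 4.0). A D of 15 points shows as 5.0 (4.0 to 6.1).

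**4. Precision if shown separately.** The 95% half-width for switchers minus never-switched in PASI-75 is 1.96 × √[p(1−p)(1/n₁ + 1/n₂)]. The 70% rate is the planning value for Week 12. The 90% rate and the retention figures are assumptions.

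| Response rate | 125 vs 250 | 87.5 vs 175 (70% retained) |
|---|---|---|
| 70% | 9.8 points | 11.8 points |
| 90% | 6.4 points | 7.7 points |

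**5. Follow-up under the pooled rule.** After Week 16, PASI is assessed at Weeks 20 and 24 (reported by sequence) and at Weeks 32, 40 and 48 (pooled): 3 of 5 visits.

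**6. Whole-study safety set.** The synopsis admits 250 + 125 = 375 subjects. Section 8.2.3 admits 250 + 250 = 500. The difference is 125/500 = 25% of subjects, all of them switchers. Neither definition gives switchers their own column: the synopsis leaves them out, and Section 8.2.3 places them under Humira.

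**The case against.** The grouping is explicit, and Sections 8.1.5, 8.2.2 and 8.2.3 agree on it. Most of the case against a stronger reading stands.

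- A reader might infer that Section 8.2.2 contradicts itself. It reads more naturally as a general rule followed at once by a specific open-label exception. The mismatch is with the synopsis, which lacks that exception. For open-label safety there is no conflict, because the synopsis names no grouping.
- A reader might infer that the switching objective goes unmet. The documents do not establish that. Section 2 places switching beside the 24-week comparison and gives Period 3 its own long-term aim. Week 20 and 24 efficacy and Period 2 safety are already reported by sequence. In Period 3 no one remains on Humira as a comparator, and grouping by Period 2 drug usefully isolates subjects new to CHS-1420 at Week 25.
- A reader might infer that every safety display reaching Period 3 pools switchers with never-switched subjects. It does not: the whole-study table in Section 8.2.3 uses Period 1 drug, which separates the two.
- The dilution figure restates the allocation ratio and is not evidence of harm. At a 70% response rate the half-width of a separate contrast (9.8 to 11.8 points) is about as large as the 10-point illustration.
- Sequence is fixed at randomisation, so the tables could be produced later.

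These points limit the consequence. They do not reconcile the synopsis with Section 8, and they do not give switchers a column after Week 24. Sequence tables first specified after unblinding would be post hoc.

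**Conclusion.** The point holds as a matter of alignment and reporting, at the level of something to consider. Three things are established from the text:

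1. Section 8 leaves switchers without a separate summary after Week 24. They form one third of the pooled column under 2:1:1 allocation and equal retention (27% to 40% under the assumed unequal retention).
2. The synopsis and Section 8 give different groupings for open-label efficacy.
3. The synopsis and Section 8.2.3 define different whole-study safety sets, with a Humira column of about 125 or about 250 at planned numbers and with no loss before Period 2.

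Confidence is high on the wording. It does not extend to any actual difference in switchers, whose size is hypothetical. Period 3 efficacy summaries are descriptive and open-label, safety has no inferential analysis, and the primary analysis is unaffected. The antibody wording in Section 8.2.4 needs clarification only.

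**What to change.** - **Sections 8.1.5, 8.2.2 and 8.2.3:** present Period 3 efficacy and safety by the three Period 1/Period 2 sequences, plus overall. For safety and antibodies use the sequence received, in keeping with the actual-treatment basis in Sections 8.1.3, 8.2.3 and 8.2.4. Give the number randomised and the number entering Period 3 for each sequence; Section 8.2.1 promises disposition but does not say by sequence. Label the displays descriptive and conditional on PASI-50 at Week 24.
- **Synopsis:** bring the open-label efficacy grouping into line with Section 8.
- **Synopsis and Section 8.2.3:** state one whole-study safety set, in the same words in both places.
- **Section 8.2.4:** as a clarification, name the sequence-received grouping for antibodies at Weeks 32, 40 and 48.

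Three sequence columns keep the Humira/Humira group separate, so the pooled CHS-1420 column can still be rebuilt from them. The cost is one extra column, with smaller groups, in descriptive tables, plus the wording changes. No new data are needed, and there is no effect on power or on the primary analysis.

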8.2.3 Safety Analysis

Safety data will be summarized and listed. No inferential statistical analyses of the safety data are planned. All safety summaries and listings will be generated using the Safety Population based upon treatment received for the Treatment Period of interest.

Safety data through Week 16 will be presented by the treatment received (CHS-1420 or Humira). Safety data for the study as a whole will be presented for subjects receiving CHS-1420 during Treatment Period 1 and those receiving

Humira during Treatment Period 1. Separate summaries will also be presented for Treatment Period 2 based upon the particular treatment sequence received in Treatment Periods 1 and 2: CHS-1420/CHS-1420, Humira/Humira and Humira/CHS-1420.

Safety data for the open label extension will be summarized separately. The primary focus of these summaries will be events that are recorded after beginning open-label treatment and events that began in Treatment Period 1 or 2 and worsen in severity in Treatment Period 3. The events will be summarized by treatment received in Treatment Period 2 and overall.

Adverse events will be coded and classified by system organ class and preferred term using the Medical Dictionary for Regulatory Activities (MedDRA). Data summaries will be based on TEAEs. All TEAEs will be listed and summarized by the subjects' treatment group (Treatment Period specific) when the events were reported. A summary of all drug-related AEs will also be generated. If there are any SAEs or any AEs leading to the discontinuation of study drug, a separate data listing will be generated.

Clinical laboratory data will be summarized descriptively and listed by treatment (Treatment Period specific) group. The change from pre-dose to the end of the study will also be summarized. For selected laboratory assessments, the frequency of abnormal values will be tabulated where abnormal ranges are available.

Prior and concomitant medications will be coded with the World Health Organization Drug Dictionary (WHO-DD) and listed. All concomitant medication taken after first dosing of study drug will be summarized.

Vital sign and ECG data will be summarized and listed by dose group and visit.

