STUDY TITLE: A Double-Blind, Randomized, Parallel-Group, Active Control Study to Compare the Efficacy and Safety of CHS-1420 Versus Humira® in Subjects With Chronic Plaque Psoriasis (PsOsim)

INVESTIGATOR

By signing below I agree that:

I have read this protocol and agree to conduct the study as outlined herein in accordance with International Conference on Harmonisation Good Clinical Practice, United States Food and Drug Administration regulations, Institutional Review Board regulations, and regional regulatory requirements.

Principal Investigator Signature

Date

Principal Investigator Name and Title (please print)

Institution Address

Confidentiality Statement

The information in this document is confidential and is not to be disclosed without the written consent of Coherus BioSciences, Inc. except to the extent that disclosure would be required by law and for the purpose of evaluating and/or conducting a clinical study for Coherus BioSciences, Inc. You are allowed to disclose the contents of this document only to your Institutional Review Board/Ethics Committee and study personnel directly involved with conducting this protocol. Persons to whom the information is disclosed must be informed that the information is confidential and proprietary to Coherus BioSciences, Inc. and that it may not be further disclosed to third parties.

SYNOPSIS

Study Title	A Double-Blind, Randomized, Parallel-Group, Active Control Study to Compare the Efficacy and Safety of CHS-1420 Versus Humira® in Subjects With Chronic Plaque Psoriasis (PsOsim)
Sponsor	Coherus BioSciences, Inc.
Study Objectives	
Primary Objective: To compare the efficacy (measured by the Psoriasis Area and Severity Index [PASI]) and safety of CHS-1420- and Humira sourced from the United States (US) at 12 weeks in subjects with moderate to severe chronic plaque psoriasis (PsO)
 
Secondary Objectives: To compare the safety of and durability of response to CHS-1420 and Humira over 24 weeks as well as efficacy/safety of switching from Humira to CHS-1420. To assess long term safety and efficacy of CHS-1420 during the open label extension over a further 24 weeks (Treatment Period 3).

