2 STUDY OBJECTIVES

The primary objective of this study is to compare the efficacy (measured by the Psoriasis Area and Severity Index [PASI]) and safety of CHS-1420 and Humira at 12 weeks in subjects with moderate to severe chronic PsO. The secondary objectives are to compare the safety of and response to CHS-1420 over 24 weeks as well as efficacy/safety of switching from Humira to CHS-1420. Long term safety and efficacy of CHS-1420 during the open label extension over a further 24 weeks (Treatment Period 3) will be assessed.

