4.3 Method of Assigning Subjects to Treatment Groups

Once the subject has signed the ICF at Screening, site personnel will assign a subject identification number (ID). The subject ID will include the site number (3 digits), and 3 digit subject number, assigned sequentially starting with 001. This number will be utilized to identify the subject throughout the study period. Once the subject ID has been assigned, the site will contact the Interactive Voice Response System/Interactive Web-based Response System (IXRS) to register the subject ID. Dropouts (subjects who discontinue study treatment early, and subjects who are randomized but not treated) will not be replaced. No individual is allowed to re-enter the study if previously randomized and dosed.

Subjects will be assigned to study drug in accordance with the randomization schedule generated using permuted block randomization by an independent statistician.

Approximately 500 subjects will be randomly assigned in a 1:1 ratio (approximately 250/arm) to receive 1 of the following treatments in Treatment Period 1:

- 2 SC injections (2 pre-filled syringes, [80 mg]) of Humira on Week 0/Day 0 and 1 SC injection (1 pre-filled syringe [40 mg]) of Humira QOW from Week 1/Day 7 through up to Week 15/Day 105.
- 2 SC injections (2 pre-filled syringes, [80 mg]) of CHS-1420 on Week 0/Day 0 and 1 SC injection (1 pre-filled syringe [40 mg]) of CHS-1420 QOW from Week 1/Day 7 through up to Week 15/Day 105.

Subject randomization will be stratified by body mass index (BMI) (less than ($<$) 30 kg/m² or greater than or equal to (\geq) 30 kg/m²), age (<65 yrs or ≥ 65 yrs) and region.

At the end of Treatment Period 1 (Week 16), subjects taking Humira will either begin dosing with CHS-1420 or continue with Humira during Treatment Period 2. A single randomization will be used to determine treatment in Treatment Periods 1 and 2. In effect, a 2:1:1 randomization will be used where for each 2 subjects randomized to receive CHS-1420 an additional 2 will be assigned to receive Humira in Treatment Period 1. For the subjects assigned to Humira in Treatment Period 1, 1/2 of these will be randomly assigned to continue with Humira for Treatment Period 2 and 1/2 will be assigned to switch to CHS-1420 for Treatment Period 2.

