At the end of Treatment Period 2 (Week 24), all subjects that achieve at least a PASI-50 score will be assigned CHS-1420 for Treatment Period 3 and continue QOW administration from Week 25/Day 175 through Week 47/Day 329.

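### Section 8.2.3 and the synopsis group the whole-study safety table differently; run through Period 3, both put CHS-1420 time in the Humira column, and no clean Week 0–24 safety table is planned

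*Combined protocol and SAP*

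**What the plan says.** Section 8.2.3 defines the whole-study display by the drug taken in Period 1: "Safety data for the study as a whole will be presented for subjects receiving CHS-1420 during Treatment Period 1 and those receiving" Humira in that period. It does not say what span the whole study covers.

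The synopsis, under Statistical Analysis, describes the same display with a stated span and different groups: "time spanning Treatment Periods 1 to 3) will be presented for those randomized and receiving the same treatment in Treatment Periods 1 and 2". Only the CHS-1420/CHS-1420 and Humira/Humira sequences meet that condition.

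Section 4.3 uses a single 2:1:1 randomization. Of the subjects given Humira first, "1/2 of these will be randomly assigned to continue with Humira for Treatment Period 2", and the other half switch to CHS-1420. After Week 24, "all subjects that achieve at least a PASI-50 score will be assigned CHS-1420 for Treatment Period 3".

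Section 8.2.3 also says that treatment-emergent events are summarized by the subject's "treatment group (Treatment Period specific) when the events were reported". The other planned displays are:

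- safety through Week 16 by drug received;
- Period 2 by sequence ("Separate summaries will also be presented for Treatment Period 2 based upon the particular treatment sequence received in Treatment Periods 1 and 2");
- the open-label extension, separately, by Period 2 treatment and overall.

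The synopsis sets a secondary objective, "To compare the safety of and durability of response to CHS-1420 and Humira over 24 weeks". Section 2 has the same 24-week horizon but does not name Humira in that clause: "The secondary objectives are to compare the safety of and response to CHS-1420 over 24 weeks".

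**The concern.** The two texts cannot both be programmed. Under Section 8.2.3 the switchers make up half of the Humira column; under the synopsis they appear in no column of this table.

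Section 8.2.3 is also unclear within itself. If a switcher has an event at Week 20, the period-specific rule assigns it to CHS-1420, while a column fixed by Period 1 drug assigns it to Humira. No precedence is given.

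Whichever grouping is used, a table that runs through Period 3 counts CHS-1420 treatment time under a Humira label. In a biosimilar comparison this errs in the unhelpful direction, because it makes the two products look more alike than they are. The whole-study table is also the only cumulative safety display planned beyond Week 16, so the 24-week safety objective has no cumulative display that is both defined and unmixed.

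**Working it through.** The documents state no figure for this table, so there is none to reproduce. The check is arithmetic on treatment weeks.

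**Inputs**

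- About 500 subjects (Section 8.3), allocated 2:1:1 (Section 4.3): about 250 CHS-1420/CHS-1420, 125 Humira/Humira and 125 Humira/CHS-1420. Switchers are 125/500 = 25% of the trial.
- Period lengths of 16, 8 and 24 weeks (synopsis, Study Duration).
- *e*, the fraction of Humira-arm subjects who enter and complete Period 3. Entry requires PASI-50 at Week 24 and the documents give no rate, so *e* is varied from 0.5 to 1.
- Full retention to Week 24 is assumed. Follow-up time after the last dose is not counted.

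**CHS-1420 share of the Humira column**

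Under Section 8.2.3, half the column spends 8 weeks on CHS-1420 in Period 2, an average of 4 weeks per subject. Everyone who enters Period 3 adds 24 weeks:

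- Section 8.2.3: s = (4 + 24e) / (24 + 24e)
- Synopsis (no switchers): s = 24e / (24 + 24e)

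| Span | Section 8.2.3 | Synopsis |
|---|---|---|
| Weeks 0–24 only (e = 0) | 4/24 = 17% | 0% |
| Periods 1–3, e = 0.5 | 16/36 = 44% | 12/36 = 33% |
| Periods 1–3, e = 0.8 | 23.2/43.2 = 54% | 19.2/43.2 = 44% |
| Periods 1–3, e = 1 | 28/48 = 58% | 24/48 = 50% |

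In person-weeks at full entry these are 7000/12000 and 3000/6000. Counting scheduled injections instead (10, 4 and 12 per period) gives (2 + 12)/26 = 54% and 12/26 = 46%.

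**Illustration of dilution**

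Assume constant event rates and a display based on exposure. A true CHS-1420:Humira rate ratio R then appears as R / ((1 − s) + sR). For an assumed R = 2.0:

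- Section 8.2.3, Weeks 0–24: 2/(1 + 0.167) = 1.71
- Section 8.2.3, e = 0.8: 2/(1 + 0.537) = 1.30
- Synopsis, e = 0.8: 2/(1 + 0.444) = 1.38

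It stays 2.0 in the Week 16 table and between the two unswitched sequences in the Period 2 table.

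**Can the period tables be added to give Weeks 0–24?**

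No. The Week 16 table pools both Humira sequences, and a subject with events in both periods would be counted twice. If 40% had an event in Period 1 and 25% in Period 2 (assumed), cumulative incidence could lie anywhere from max(40%, 25%) = 40% to 40% + 25% = 65%.

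**The case against.** The strongest reply is that the largest Section 8.2.3 figures join its groups to a span stated only in the synopsis. Section 8.2.3 does not define its span and summarizes the extension separately, so it could be read as stopping at Week 24. That stands as a limit on the 44% to 58% range. On that reading the share is 17%, and the conflict with the synopsis remains.

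Second, Section 8.2.3 bases safety summaries on treatment received in the period of interest, which shows an intent to attribute by period. That protects the single-period tables. It does not say how to build a table that spans several periods, which has no one period of interest.

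Third, following subjects by initial treatment is a legitimate descriptive display when its basis is disclosed. This is fair, but such a table is not a comparison of CHS-1420 with Humira over 24 weeks.

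Fourth, the Week 16 and Period 2 tables together cover 24 weeks without mixing drugs, and events are also listed. This is true and it narrows the gap. What is missing is a single cumulative incidence by sequence that counts each subject once.

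Finally, the rate ratios and event percentages are illustrative, the plan does not commit to exposure-based rates, and no safety test is planned. These points limit the consequence. They do not remove the contradiction.

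**Conclusion.** The concern holds and should be fixed. The grouping conflict and the absence of an unmixed cumulative Week 0–24 table follow directly from the text. The size of the mixing depends on the span. It is 17% (Section 8.2.3) or 0% (synopsis) if the table stops at Week 24. Through Period 3 it is 44% to 58% or 33% to 50%, given full retention to Week 24 and an assumed 50% to 100% entering and completing Period 3.

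The consequence is confined to one descriptive display. Type I error, power and the primary efficacy result are untouched, and the unmixed Week 16 table covers the 12-week primary safety comparison.

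**What to change.** Use the same rule and the same stated time span in Section 8.2.3 and the synopsis, and settle both before unblinding.

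- Present cumulative safety from Week 0 to Week 24, before any open-label dose, for CHS-1420/CHS-1420 versus Humira/Humira, with Humira/CHS-1420 as a third column. This is the synopsis grouping stopped at Week 24 with the switchers added, and it matches the by-sequence convention that Section 8.2.2 already uses for efficacy. The Humira/Humira column then holds no CHS-1420 time.
- Keep the Week 16 table with the full arms.
- For any table running past Week 24, either label the columns by sequence or attribute events and exposure to the product taken at onset, with exposure-adjusted rates. Describe it as descriptive and not a randomized comparison of the two products, because Period 3 time is later and limited to PASI-50 responders.
- State that the period-specific rule for treatment-emergent events does not apply to columns defined by sequence.

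The cost is wording in two places and revised table shells, with no new data. The Humira/Humira column has about 125 subjects instead of 250. For an event with an assumed 10% incidence, the 95% half-width for the difference rises from 1.96 × √(0.09 × (1/250 + 1/250)) = 5.3 percentage points to 1.96 × √(0.09 × (1/250 + 1/125)) = 6.4. The Week 16 table keeps full-arm precision.
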